5.2.4 Integrative Sessions 24 Hours after Experimental Session

The subject and support partner (if applicable) will receive pagers (or similar device) that will allow them to contact the therapists during the period after the first in-person office visit following treatment sessions in the case of an emergency or request for additional support. Subjects will be encouraged to use much of the time during the 24-hours post-session for rest and for a period of reflection and integration in a quiet atmosphere. On the morning after each experimental session, the therapists will meet with the subject for a 60-minute integrative therapy session.

Activities during these sessions include discussing material that emerged during experimental sessions and helping subjects integrate their experiences both internally and into daily life. Therapists will validate the choices of the subject about how much they wish to communicate their thoughts, feelings, and experiences at this time, but will elicit enough information to be able to assess the subject's level of emotional stability and state of emotional and physical wellbeing. Therapists will emphasize their commitment to support the subject during the integration period and will be available via phone for additional meetings if needed. Subjects will be encouraged to relax and rest as much as possible for several days after the experimental session.

During integrative sessions:

- a. The integrative session may be recorded to audio and video. Subjects may receive access to copies of the recordings on a secure, password-protected website upon request.
- b. The therapists will administer the C-SSRS during each integrative session.
- c. The subject and both therapists will indicate their beliefs concerning subject condition assignment.
- d. Discuss and review events that occurred with the subject during the experimental session, including thoughts, feelings, and memories. If necessary, the therapists will help the subject to reduce any residual psychological distress he or she is experiencing. The therapists will also encourage the transfer of states of acceptance, feelings of intimacy, closeness, and reduced fear experienced in

- experimental sessions to emotionally threatening everyday situations. The therapists will be supportive, validating the experience, and facilitating understanding and emotional clearing.
- e. The therapists will remain accessible any time the subject needs support outside the scheduled integration sessions.
 - f. Assess the subject's mental health and the presence of any remaining reactions during the integrative session.
 - g. Integrative sessions can also serve as an opportunity for the therapists to gather information about the effects of the drug on the subject in an unstructured manner.
 - h. At the end of the session, subjects will complete:
 - a. BDI-II
 - b. STAI
 - i. The IR will administer the LSAS.
 - j. Spontaneously reported reactions, AEs, and concomitant medications will be collected, as described in Section 8.5 and Section 9.0.
 - k. Assess status of symptoms at baseline specific to the study population.
 - l. After the integrative session, a person previously selected by the subject will provide a ride home to the subject. If the subject is unable to locate an individual willing or able to take him or her home, or if the designated person is unable to assist the subject due to unforeseen events, the therapists will assist the subject in finding an alternative means of returning home.
 - m. Remind the subjects that they will have daily phone contact for the next seven days.

5.2.5 Daily Contact for Seven Days after an Experimental Session

During daily contact:

- a. Starting on the day of the integrative session following each experimental session, one of the therapists will contact the subject via telephone or email on a daily basis for seven days. The goal of daily contact is assessment of changes in general wellbeing, safety of the subjects, and offering support for subjects.
- b. The integrative phone contact will be for a brief check-in lasting five to fifteen minutes or as long as necessary to address any concerns a subject has and to assess subject's wellbeing. Additional telephone contact can be initiated at the request of the therapists or subject.
- c. On the second and seventh day of contact after the experimental session, one of the therapists will administer the C-SSRS.
- d. General wellbeing will be assessed at each phone call.
- e. Assess status of symptoms at baseline specific to the study population.
- f. Spontaneously reported reactions, AEs, and concomitant medications will be collected, as described in Section 8.5 and Section 9.0.

5.2.6 Biweekly Integrative Sessions

In addition to the integrative session the morning after each experimental session, the subject will have two additional integrative sessions with the therapists lasting 60 minutes

with the therapists between each experimental session scheduled at two-week intervals following the last integrative session. The therapists may conduct more or longer integrative sessions if they and the subject deem it necessary.

Activities for these sessions include integration of material that emerged as a part of experimental sessions and afterward into daily life. Therapists will emphasize their commitment to support the subject during the integration period and will be available via phone or pager.

During integrative sessions:

- a. Record each integrative session to audio and video. Subjects may receive access to copies of the recordings on a secure, password-protected website upon request.
- b. The C-SSRS will be administered just prior to beginning each integrative session.
- c. General wellbeing will be assessed at each integrative session.
- d. The subject and therapists will continue to work on supporting the subject as she or he considers his or her experiences during experimental sessions.
- e. The therapists will use clinical judgment to assess the subject's psychological wellbeing during this period of time. If there are any indications of continuing anxiety or distress, the therapists may arrange to work on reducing the distress at a specially scheduled integrative session, through continuing contact, or at the next regularly scheduled integrative session. The subject may also initiate contact with the therapists at any time throughout the study.
- f. At the second integrative session after the second experimental session, blood will be drawn for biomarker analysis.
- g. At the second integrative session after the second experimental session, collect information on phase of menstrual cycle for female subjects.
- h. At the beginning or end of each integrative session, subjects will complete:
 - a. BDI-II
 - b. STAI
- i. At the beginning or end of each integrative session, the IR will administer the LSAS.
- j. At the beginning or end of the third integrative session, subjects will also complete:
 - a. ERQ
 - b. TAS-20
 - c. TASIT
- k. Spontaneously reported reactions, AEs, and concomitant medications will be collected, as described in Section 8.5 and Section 9.0.
- l. Assess status of symptoms at baseline specific to the study population.
- m. Remind the subject that the last integrative session in Stage 1 that this will be the last in-person visit prior to the 6-month Follow-up visit, and that some measures will be collected monthly by mail.
- n. Review how to use the Memory Aid Card with the subject. Subjects will use this card to record AEs, medications, and changes in psychiatric status that they will be asked about at the 6-month follow-up visit. Memory Aids will not be collected.

5.2.7 6-Month Follow-up

Subjects who have withdrawn from treatment but have continued for follow-up will also complete these assessments whenever possible. During the follow-up period:

- a. Subjects may return to taking psychiatric medications or change frequency or method of psychotherapy received from outside therapists if necessary.
- b. The following self-report measures will be completed by subjects and collected monthly at two, three, four, and five months after the second experimental session by mail:
 - a. BDI-II
 - b. STAI
 - c. PSS
- c. At the 6-month follow-up, an in-person visit will be conducted.
- d. The IR will administer the LSAS.
- e. Collect information on phase of menstrual cycle for female subjects.
- f. Blood will be drawn for biomarker analysis.
- g. Subjects will complete self-report outcome assessments, including:
 - a. ERQ
 - b. TAS-20
 - c. TASIT
 - d. QoL-Q
 - e. RSES
 - f. IRI
 - g. BDI-II
 - h. STAI
 - i. PSS
 - j. Feedback Questionnaire
- h. Review specified AEs and medications as described in Section 8.5 and Section 9.0. Subjects should bring the Memory Aid Cards to this visit, to be used as aids in recollection. These cards will not be collected.
- i. Assess status of symptoms at baseline specific to the study population.
- j. One of the therapists will assess suicidality with the C-SSRS.
- k. General wellbeing will be assessed.
- l. The therapists will review the responses to the Feedback Questionnaire assessing effects of the study with the subject. During the qualitative interview, additional follow-on questions may be asked to elucidate self-reported responses on the questionnaire.
- m. After all assessments are complete, the therapists will break the blind for the individual subject.
- n. Subjects who were randomized to the MDMA group will complete the termination visit at this time.
- o. Subjects who were randomized to the placebo group will be offered participation in Stage 2 with open-label MDMA.

5.2.8 Open-Label Stage 2

During Stage 2:

- a. Subjects will be reminded that participation in Stage 2 is voluntary and optional.
- b. Subjects who elect to cross over to Stage 2 will undergo the same course of therapy and evaluation as in Stage 1, but with 75 mg MDMA during the first experimental session and will escalate to 125mg MDMA during the second experimental session, unless contraindicated.
- c. Subjects will have the same sequence of experimental sessions and integrative sessions as subjects receiving MDMA in Stage 1 in an open-label context. Visits will be scheduled consecutively according to the Time and Events Table.
- d. The same outcome measures completed by subjects receiving full dose MDMA in Stage 1 will be administered during Stage 2.
- e. The same safety measures as those in Stage 1 will be administered during Stage 2.
- f. Biomarker samples will be collected 2 hours after drug administration during both experimental sessions and one month after both experimental sessions during Stage 2.
- g. Stage 2 subjects will not complete an additional 6-month follow-up.
- h. Stage 2 subjects will complete the termination visit at the end of the final integrative session.

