An overnight stay at a hotel located close to the site will be offered to subjects, accompanied by their support partners, if they live further than 30 miles from the site. Subjects will attend a 1-hour follow-up integrative therapy session on the day after the experimental session. Two additional integrative sessions will be conducted within the month following each experimental session, prior to outcome assessments being conducted one month after each experimental session. During integrative therapy sessions subjects will receive support in integrating their experiences and insights from the experimental session. The second experimental session will be scheduled approximately one month after the first experimental session, after outcome assessments have been completed.

All subjects, even those who have a prior diagnosis, will be clinically evaluated by the PI to determine autistic status. In addition, autistic status will be confirmed with the gold-standard diagnostic measure of autism and diagnosis of co-morbid psychological disorders will be conducted according to DSM-IV criteria at screening. Outcome measures will be assessed prior to treatment, during the treatment period, one month after each experimental session, and during the 6-month follow-up according to the Time and Events table. The sponsor will conduct an ongoing review of videos of therapy sessions, entry criteria, vital signs, and reaction data for completed sessions and any AEs. The sponsor will provide ongoing feedback to the co-therapist teams to ensure subject safety.

For all subjects blood samples will be obtained for biomarker analysis at baseline and during the study according to the Time and Events Table. Biomarker analyses including plasma OT, AVP, and CORT will be explored as surrogate endpoints at baseline, two hours after drug administration during the second experimental session, one month after the second experimental session, and at 6-month follow-up. Blood will be collected during the open-label extension Stage 2 two hours after drug administration during both

experimental sessions and one month after both experimental sessions. Biomarkers will be evaluated for predictive and prognostic power.

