5.2.3 Experimental sessions

Subjects will receive two blinded experimental sessions of therapy assisted by MDMA or placebo, scheduled one month apart after integrative sessions are complete. Procedures for drug-assisted therapy will remain the same across all sessions. During experimental sessions, there will be periods of structured and unstructured interactions. The structured interactions will be selected based on elements of therapeutic interventions that are currently in use in this population for the treatment of social anxiety. Structured interactions during experimental sessions are intended to develop the therapeutic relationship between subjects and therapists and to enhance skills of social perception through administration of the TASIT. The unstructured interactions will include an array of therapeutic activities and approaches that would be appropriate for subjects to engage in during experimental sessions. All subjects will follow the same schedule of structured alternating with unstructured periods but will be able to choose from a selection of activities during each unstructured period. Examples include, but are not limited to, working with art supplies, listening to preselected music, writing in journals, silent introspection, and engaging in rapport-building interactions with therapists. The therapists will create and communicate a setting of safety and support the subject during periods of inner focus. Therapists will use a largely nondirective approach. Therapists will provide encouragement for staying present with difficult experiences. Therapists may occasionally offer gentle guidance or redirection as a choice to encourage collaborative exploration if the subject repeatedly avoids interpersonal contact. Therapists will use music to support the experience without being intrusive.

Table 4. Schedule of Procedures for Experimental Sessions

Approximate Time	Procedure or Action
------------------	---------------------

9:00	Urine drug screen and pregnancy test. Subject acclimated to environment, C-SSRS
9:45	Baseline Blood Pressure (BP), Pulse, SUD
10:00	MDMA Administration , begin recording to audio and video
11:00	BP, Pulse, SUD, BT
12:00	BP, Pulse, BT, SUD, During 2 nd exp. session only: Blood draw
12:15	Start TASIT (EET, SM-I, SM-E)
13:00	BP, Pulse, BT, SUD
14:00	BP, Pulse, BT, SUD
15:00	BP, Pulse, BT, SUD
16:00	BP, Pulse, BT, SUD, C-SSRS, General Wellbeing
17:00	BP, Pulse, BT, SUD, End of session

Pre-drug:

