Biomarkers will be evaluated for predictive and prognostic power. Separate estimates of effect size will be performed for OT, AVP and CORT. Changes in biomarker concentrations from pre-treatment levels will be used to analyze effects of acute dosing and to determine the time-course of elevated OT and AVP levels post-drug. Pre-treatment biomarker concentrations will be evaluated for predictive power using an exploratory hierarchical regression analysis with condition assignment in Stage 1 and biomarker concentrations at baseline as predictors and treatment outcomes as dependent variables. One regression will be performed with biomarker values taken at the second experimental session. A second regression will be performed on biomarker values taken two weeks after the second experimental session.

TAS-20 scores will be evaluated for predictive power using an exploratory hierarchical regression analysis with condition assignment in Stage 1 and TAS-20 scores at baseline as predictors and with LSAS scores as dependent measures. One regression will examine the predictive power of condition and baseline TAS-20 scores upon LSAS scores one month after the first experimental session and the other will investigate whether condition and baseline TAS-20 and will predict LSAS score at one month after the second experimental session.

Subjects who discontinue treatment prior to the second experimental session will be asked to complete the final outcome assessment prior to continuing to the 6-month follow-up whenever possible. The data from these subjects will be tested for equivalence to data from subjects completing the study per protocol. If found to be equivalent, data from these subjects will be combined for an exploratory intent-to-treat effect size estimate to examine results without bias towards subjects more likely to complete the study per protocol.

Stage 1 and Stage 2 outcomes in extension subjects will be compared after the outcome measure assessments are complete for all extension subjects.

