3.2 Secondary Objectives

The following objectives will compare MDMA and placebo groups in the blinded Stage 1:

- To assess effects on levels of oxytocin (OT), arginine vasopressin (AVP), and cortisol (CORT) in peripheral blood at baseline, once during each experimental session between hours 2 – 3, one month after the second experimental session, and at 6-month follow-up.
- To assess effects on social perception using The Awareness of Social Inference Test (TASIT) at baseline, once during each experimental session between hours 2-3, one month after the second experimental session, and at 6-month follow-up.

- To assess effects on emotion labeling using the Toronto Alexithymia Scale-20 (TAS-20) at baseline, one month after each experimental session, and 6-month follow-up.
- To assess effects on emotion regulation using the Emotion Regulation Questionnaire (ERQ) at baseline, one month after each experimental session, and 6-month follow-up.
- To assess effects on depression symptoms as measured by the Beck Depression Inventory-II (BDI-II) at baseline, one day, two weeks, one month after each experimental session, monthly by mail during the 5 months leading up to the 6-month follow-up assessment.
- To assess effects on perceptions of stress as measured by the Perceived Stress Scale (PSS) at baseline, within 24 hours after each experimental session, one month after each experimental session and monthly by mail leading up to the 6-month follow-up assessment.
- To assess effects on four aspects of empathy, as measured by the Interpersonal Reactivity Index (IRI) at baseline, within 24 hours after each experimental session, one month after each experimental session, and at the 6-month follow-up assessment.
- To assess effects on self-esteem as measured by the Rosenberg Self-Esteem Scale (RSES) at baseline, within 24 hours after each experimental session, one month after each experimental session, and at the 6-month follow-up assessment.
- To assess effects on state and trait anxiety as measured by the State-Trait Anxiety Index (STAI Form Y) at baseline, one day, two weeks, and one month after each experimental session, and monthly by mail leading up to the 6-month followup assessment.

The following objectives will compare effects in specified subjects:

- To determine if subjects who receive placebo in Stage 1 show a reduction in LSAS scores after two open-label sessions in the Stage 2 crossover

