8.10.2 Secondary Efficacy Analyses

The secondary efficacy analyses will be made with independent sample t-test comparing change from baseline (Baseline) to the primary outcome timepoint (visit 13, one month post experimental session 2) of all the secondary measures, following the same methodology used for the primary endpoint. If the parametric assumptions for the t-test analyses are not met, the analogous nonparametric methods will be used (Wilcoxon Rank Sum Test).

Liebowitz Social Anxiety Scale (LSAS) composite scores will be analyzed in the same manner as the LSAS total score primary analysis, and LSAS total score will also be analyzed for effect size with Cohen's *d* analysis.

Perceived Stress Scale (PSS) total score will be analyzed in the same manner as the LSAS total score primary analysis.

Beck Depression Inventory-II (BDI-II) total score will be analyzed in the same manner as the LSAS total score primary analysis.

Interpersonal Reactivity Index (IRI) composite scores will be analyzed in the same manner as the LSAS total score primary analysis.

Rosenberg Self Esteem Scale (RSES) total score will be analyzed in the same manner as the LSAS total score primary analysis.

State Trait Anxiety Index (STAI) subscale scores will be analyzed in the same manner as the LSAS total score primary analysis.

The Awareness of Social Inference Test (TASIT) composite and total scores will be analyzed in the same manner as the LSAS total score primary analysis.

Toronto Alexithymia Scale 20 (TAS-20) total score will be analyzed in the same manner as the LSAS total score primary analysis.

Emotional Regulation Questionnaire (ERQ) composite scores will be analyzed in the same manner as the LSAS total score primary analysis.

Quality of Life Questionnaire (QoL-Q) composite and total scores will be analyzed in the same manner as the LSAS total score primary analysis.

Biomarker (oxytocin, vasopressin, and cortisol) levels will be analyzed in the same manner as the LSAS total score primary analysis.

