8.10.3 Exploratory Analyses

Exploratory analyses of biomarkers will examine their ability to predict clinical outcome. Analyses will be performed for OT, AVP, CORT, and BDNF. Changes in biomarker concentrations from pre-treatment levels will be used to analyze effects of acute dosing and to determine the time-course of elevated biomarker levels post-drug. Pre-treatment biomarker concentrations will be evaluated in regression analysis with condition assignment in Stage 1 and biomarker concentrations at baseline as predictors and treatment outcomes as dependent variables. Additionally, the effect of biomarker levels taken at the second experimental session, and two weeks and six months after the second experimental session, will be examined for correlation with LSAS outcomes.

Distributional characteristics will be examined for outliers and extreme values. If outliers are found in primary or secondary outcome measures, the sponsor will perform analyses with and without the outlying data.

Post-hoc exploratory analyses not identified in this SAP may be performed to further examine the study data. These analyses will be clearly identified as such in the final clinical study report.

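### The post-treatment biomarker draw is timed at two weeks in some places and one month in others; the objectives also include an unscheduled session-1 draw, and the SAP analyses BDNF with no described assay

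*Protocol*

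**What the plan says.** **Post-treatment draw.** The visit procedures in Protocol 5.2.6, item f, state: "At the second integrative session after the second experimental session, blood will be drawn for biomarker analysis". Protocol 12.0 agrees on timing: "A second regression will be performed on biomarker values taken two weeks after the second experimental session". SAP 8.10.3 likewise correlates two-week biomarker values with LSAS outcomes. Protocol 4.0 instead lists the on-study samples after baseline as "two hours after drug administration during the second experimental session, one month after the second experimental session, and at 6-month follow-up", and SAP 4.0 repeats this. The secondary objectives (section 3.2 of each document) say one month, and the serology row of Protocol Table 2 is ticked at V13. SAP 8.10.2 needs V13: "Biomarker (oxytocin, vasopressin, and cortisol) levels will be analyzed in the same manner as the LSAS total score primary analysis". That primary analysis is change from baseline to V13 (SAP 8.10.1).

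**Acute draw.** Both sets of objectives call for OT, AVP and CORT "in peripheral blood at baseline, once during each experimental session between hours" 2 and 3. Protocol Table 4 restricts its noon line to the second session: "exp. session only: Blood draw". Table 2 has no serology tick at V6, the first session.

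**Analytes.** SAP 8.10.3 states: "Analyses will be performed for OT, AVP, CORT, and BDNF". Protocol 10.2 describes assays for OT, AVP and CORT only, and SAP 8.10.2 names the same three.

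**The concern.** OT, AVP and CORT are the first-listed secondary objective, and Protocol 2.3 relies on their time course to judge whether treatment produces lasting change. A sample not drawn at the right visit cannot be recovered. Site staff working from the visit procedures would draw at V12, and staff working from the Time and Events table would draw at V13. If both happened, a comparison of 8 MDMA with 4 placebo subjects would mix two timepoints. The analyst meets the same conflict inside the SAP, where 8.10.2 and 8.10.3 assume different visits. The session-1 and BDNF mismatches leave the plan committed to results that its own schedule and laboratory section do not provide for.

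**Working it through.** No power or alpha figure is involved. The check sets the texts side by side and counts draws.

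**Step 1. Which visit is the second integrative session?** Protocol Table 2 spaces the visits after session 2 (V10) at one day, then two weeks, then two weeks. V11 is therefore day 1, V12 is day 1 + 14 = 15, and V13 is day 15 + 14 = 29. In 5.2.6, item j reads "At the beginning or end of the third integrative session, subjects will also complete" and then lists the ERQ, TAS-20 and TASIT. Table 2 ticks all three at V13 and none at V12. The third session is thus V13, and the second is V12.

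**Step 2. Where each text puts the post-treatment draw.**

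| Source | Timing |
|---|---|
| Protocol 5.2.6 f | V12 |
| Protocol 12.0, second regression | two weeks |
| SAP 8.10.3, correlations | two weeks |
| Protocol Table 2 | V13 |
| Objectives, section 3.2 of both documents | one month |
| Design text, section 4.0 of both documents | one month |
| SAP 8.10.2 | V13 |

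No text describes both draws.

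**Step 3. Samples available under each literal reading (12 subjects).**

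| Draw taken at | Baseline-to-V13 test | Two-week regression and correlation |
|---|---|---|
| V12 | 0 | 12 |
| V13 | 12 | 0 |

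**Step 4. Stage 1 draw count.** The Table 2 serology row, read by column, is V2, V10, V13 and V14.

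- Scheduled: 4 × 12 = 48.
- Objectives, which add V6: 5 × 12 = 60.
- Serving every text, which adds V6 and V12: 6 × 12 = 72.

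**Step 5. Acute draws in Stage 1.**

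- Objectives: 2 × 12 = 24 (16 MDMA, 8 placebo).
- Scheduled at session 2 only: 12 (8 MDMA, 4 placebo).
- Planned session-2 doses are 100 mg in 4 subjects and 125 mg in 4. In Stage 1, 75 mg is planned only at session 1, so no blinded acute sample is planned at 75 mg.
- Stage 2 is consistent across Protocol 4.0, 5.2.8 and Table 3: draws at both sessions and one month after each (V15, V18, V19, V22). Its first session is at 75 mg, so open-label acute samples at that dose are planned in up to 4 subjects.

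**Step 6. BDNF.** It appears in SAP 8.10.3 and nowhere else in the readable text: not in an objective, a serology row, Protocol 10.2, SAP 8.10.2 or the visible abbreviation lists.

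**The case against.** The best defence is that there is one intended draw with a labelling slip. Section 5.2.6 opens by describing two further integrative sessions after the next-day one, so the second could mean the second of those, which is V13. Table 2 heads V13 as two weeks later, meaning after V12, and that could be the source of the two-week wording elsewhere. On that reading every analysis uses the V13 sample and nobody is lost. Protocol 4.0, Protocol 10.2 and SAP 4.0 also defer to the Time and Events table for sampling.

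Part of this stands. V13 is the more likely outcome in practice, so a reader who infers that an analysis will certainly lose all 12 subjects goes too far. That follows only if the texts are applied literally. The slip still needs correcting, because item j numbers the sessions the other way and the analysis texts count from the second experimental session, not from the preceding visit.

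Three other strong readings also fail:

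- **That the acute objective cannot be met at all.** Only its session-1 part is unserved; baseline, session 2, one month and six months are all scheduled.
- **That no acute sample exists at 75 mg.** Stage 2 plans open-label ones. Escalation in Stage 1 is also conditional on safety and tolerability, so the session-2 doses are planned rather than certain.
- **That BDNF has no samples or was never measured.** Protocol 10.2 stores aliquotted plasma from 30 mL draws, so an assay could be added. The documents show only that none is described.

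It is also fair that this is an uncorrected 12-subject pilot which pools doses for its effect-size estimates. That limits the weight of the blinded 75 mg gap.

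**Conclusion.** The plan is wrong as written, for secondary and exploratory biomarker analyses only. The post-treatment draw has two incompatible timings, about day 15 and about day 29, and one scheduled sample. Read literally, one set of planned analyses has no data: either the baseline-to-V13 test or the two-week regression and correlation. Half of the 24 Stage 1 acute draws in the objectives are unscheduled, including all those planned at 75 mg. One of the four analytes in SAP 8.10.3 has no described assay.

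This rests on full enrolment of 12 with escalation as planned, and on Protocol Table 2 as the Stage 1 schedule. The SAP's own Stage 1 Time and Events table was not readable in the text examined, so it was not checked. A reader might infer that the efficacy result is at risk. It is not: the primary LSAS analysis uses none of these samples.

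**What to change.** 1. In Protocol 5.2.6, change item f to the third integrative session after session 2 (V13). Move item g, the menstrual-phase record, with it; otherwise that record is taken two weeks before the sample it accompanies.
2. In Protocol 12.0 and SAP 8.10.3, change two weeks to one month for the post-treatment biomarker value.
3. In section 3.2 of both documents, limit the Stage 1 acute biomarker objective to session 2. Leave the TASIT objective alone: Table 2 does schedule it at both sessions.
4. Remove BDNF from SAP 8.10.3, unless an assay on the stored plasma is specified in Protocol 10.2.

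The cost is wording in both documents and no extra blood draw; keeping BDNF would add assay work. The downside is that the two-week and session-1 biomarker values are formally dropped. If the sponsor wants either, it must be added to the schedule: 12 more draws for each, or 72 − 48 = 24 for both.
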